6.2 DETAILS OF TRIAL PROCEDURES AT SELECTED VISITS

6.2.1 Screening and run-in period(s)

Screening Period

After having been informed about the trial, all subjects will give their written informed consent in accordance with GCP and local legislation prior to enrolment in the study.

The screening should take place no more than 28 days before Day 1.

At the screening visit, the medical examination will include documentation of subject information, informed consent, demographics including height and body weight, smoking and alcohol history, relevant medical history and concomitant therapy, review of inclusion and exclusion criteria, review of vital signs (BP, PR, and temperature), 12-lead ECG, laboratory tests, and a physical examination. Subjects who have laboratory test value (e.g., platelet count) clinically outside acceptable ranges, may have the test repeated once to determine eligibility; however, the result of re-assessment must be available prior to randomisation (Day 1).

After all general screening clinical assessments were performed, only subjects who meet eligibility criteria will undergo UV irradiation and preliminary photosafety testing will be performed.

Boehringer Ingelheim

BI Trial No.: 1407-0037

c27983101-03 Clinical Trial Protocol Page 60 of 79

Proprietary confidential information © 2020 Boehringer Ingelheim International GmbH or one or more of its affiliated companies

The preliminary photosensitivity examination will be performed no later than Day -3, followed by the base line irradiation and photosensitivity assessments stariting on day -2.

Baseline Conditions

Subjects eligible for the study participation will be admitted to the clinical site on day -1, and check of In/Exclusion criteria as well as Base-line photosensitivity assessment will be performed.

If possible, spare subjects will be provided for each group to guarantee the start of a complete group. The spare subjects will participate in all trial activities up to Day 1, i.e. on Day -1 they will be admitted to the clinic and all examinations, which have been scheduled up to drug administration on Day 1 will be performed. The spare subjects from one group will be given the option to participate in the next planned group.

6.2.2 Treatment period(s)

Treatment A

Subjects will be randomized in the morning on Day 1 and receive 400mg of BI 730357 or placebo once daily over 8 days, or 300mg of BI 730357 or placebo twice daily 12 hours apart over 8 days with the single dose on day 8, in order to reach pharmacokinetic steady state;

UVB/UVA irradiation will occur 2 hours after the last dose of either IP or placebo, and photosensitivity assessments (determination of MED_{On drug} and evaluation of erythema/local skin reactions) will be performed at 10 (+/- 2) minutes, and 1 (+/- 5 min), 24(+/- 10 min)

Treatment B

Subjects will receive their first dose of 500 mg ciprofloxacin on the morning of Day 3. Twelve (12) hours later, subjects received their second dose of 500 mg ciprofloxacin. Subjects continued a twice-daily dosing regimen through to the morning of Day 8 to ensure they have reached pharmacokinetic steady state

UVB/UVA irradiation will occur 2 hours after the last dose of Ciprofloxacin, and photosensitivity assessments (determination of MED_{On drug} and evaluation of erythema/local skin reactions) were performed at 10 (+/- 2) minutes, and 1(+/- 5 min), 24(+/- 10 min),

For details on time points for all other trial procedures, refer to the Flow Chart. AEs and concomitant therapy will be assessed continuously from screening until the end of trial examination.

01 Apr 2020

c27983101-03 Clinical Trial Protocol Page 61 of 79

Proprietary confidential information © 2020 Boehringer Ingelheim International GmbH or one or more of its affiliated companies

6.2.3 Follow-up period and trial completion

End of Trial

Subjects who completed the treatment according to the protocol, as well as subjects who discontinued treatment before the end of the planned treatment period should undergo the end of trial visit 7 days after last intake of the study medication.

For AE assessment, laboratory tests, recording of ECG and vital signs, and physical examination during the end of trial refer to the Flow charts.

All abnormal values (including laboratory parameters) that are judged clinically relevant by the Investigator will be monitored using the appropriate tests until a return to a medically acceptable level is achieved. (S)AEs persisting after subject's end of trial must be followed up until they have resolved, have been sufficiently characterized, or no further information can be obtained.

The end of the trial as a whole is defined by the 'last regular visit completed by last subject' or 'end date of the last open AE' or 'date of the last follow-up test' or 'date of an AE has been decided as sufficiently followed-up', whichever is latest.

c27983101-03 Clinical Trial Protocol Page 62 of 79

Proprietary confidential information © 2020 Boehringer Ingelheim International GmbH or one or more of its affiliated companies

7. STATISTICAL METHODS AND DETERMINATION OF SAMPLE SIZE

The objective of this trial is to investigate the photosensitivity under three distict exposure conditions of BI 730357 following 8 days of administration (i.e. steady state) on the basis of the primary and secondary endpoints. The trial is designed to allow comparisons between BI 730357 and placebo as well as BI 730357 and a positive control (ciprofloxacin). These comparisons will be evaluated statistically by use of a mixed model for repeated measures.

Each double blind randomization group (Part A: BI 730357 400 QD/placebo and BI 730357 300 BID/placebo) will be analysed separately for the assessment of photosensitivity.

7.1 NULL AND ALTERNATIVE HYPOTHESES

BI 730357 vs placebo

The assessment for absence of photosensitivity will be based upon the differences in mean photosensitivity index (PI) between BI 730357 and placebo two-sided 90% confidence intervals (CIs) for the differences in the photosensitivity index (Section 7.2.2) between BI 730357 and placebo using an acceptance range of -0.4 to 0.4. This method is equivalent to the two-sided t-test procedure, each at the 5% significance level.

The following comparisons will be performed:

- BI 730357 400 mg QD vs placebo 400 mg QD
- BI 730357 300 mg BID vs placebo 300 mg BID

The following hypotheses are tested:

Null hypothesis H₀ (Photosensitive): $\mu_{BI} - \mu_{pbo} \le -\delta \ or \ \mu_{BI} - \mu_{pbo} \ge \delta$

Where μ_{BI} and μ_{pbo} are the means of the endpoint for BI 730357 and placebo, respectively, and δ is the limit that defines the acceptance range for photosensitivity equivalence.

Alternative hypothesis H_a (Absence of photsensitivity): $-\delta < \mu_{BI} - \mu_{pbo} < \delta$

In this trial, the equivalence limit δ is 0.4 which is consistent with historical criteria used for positive photosensitivity for a drug (R19-3037).

The rejection of the null hypothesis at the $\alpha = 0.05$ level is equivalent to the inclusion of the 90% confidence interval for μ_{BI} - μ_{pbo} in the acceptance range (- δ , δ).

Although there are multiple endpoints where the photosensitivity index will be statistically compared, an alpha adjustment is not needed because it is required that all endpoints meet the equivalence criterion as described above simultaneously.

c27983101-03 Clinical Trial Protocol Page 63 of 79

Proprietary confidential information © 2020 Boehringer Ingelheim International GmbH or one or more of its affiliated companies

BI 730357 vs ciprofloxacin, Placebo vs ciprofloxacin

Comparisons between the mean PI between BI 730357 and ciprofloxacin as well as between placebo and ciprofloxacin at the different timepoints under conditions 1 and 2 will be performed.

The planned comparisons are:

- BI 730357 400 mg QD vs ciprofloxicin
- BI 730357 300 mg BID vs ciprofloxicin
- Placebo for 400 mg QD vs ciprofloxicin
- Placebo for 300 mg BID vs ciprofloxicin

At each timepoint the null hypothesis will be that there is no difference in the mean PI of BI 730357 compared to ciprofloxacin:

Null hypothesis H_0 : $\mu_{BI/pbo} - \mu_{cipro} = 0$

Where $\mu_{BI/pbo}$ and μ_{cipro} are the means of the endpoint for BI 730357 or placebo and ciprofloxicin, respectively

The alternative hypothesis will be that the means are not equal:

Alternative hypothesis H_a : $\mu_{BI/pbo}$ - $\mu_{cipro} \neq 0$

A significant finding of increased photosensitivity of ciprofloxacin compared to BI 730357 and to placebo at the p<0.05 level will be supportive in concluding that the trial was appropriately designed to test the photosensitivity of BI 730357.

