7.5 DETERMINATION OF SAMPLE SIZE

It is planned to include initially a total of 84 healthy male and female subjects (36 subjects for Treatment A 400 mg QD, 36 subject for Treatment A 300 mg BID; 12 subjects for Treatment B) in this trial.

The planned numbers of subjects should be sufficient for the exploratory evaluation of photosafety of each of the BI 730357 dose groups. Based on a similarly designed study for evaluation of pradigastat the observed mean (standard deviation) over all PI measurements for 9 patients who received placebo and 12 subjects who received ciprofloxacin was 1.08 (0.12) and 1.61 (0.55), respectively (R19-3037).

Assuming a common standard deviation of 0.15 and an expected difference in mean PI of 0 between BI 730357 and placebo, each of the two group 0.05 one-sided t-tests will have 99% power to reject the null hypothesis that BI 730357 and placebo are not equivalent (the difference in means, μ_{BI} - μ_{pbo} , is \geq 0.4 and μ_{BI} - $\mu_{pbo} \leq$ -0.4) in favor of the alternative hypothesis that the means of the two groups are equivalent (nQuery Advisor, version 7).

Additionally, for the planned comparison of mean PIs for BI 730357 and ciprofloicin, a two group Satterthwaite t-test with a 0.05 two-sided significance level will have 87% power to detect a difference in means of 0.6 (the difference between μ_{cipro} of 1.60 and a μ_{BI} of 1.0) assuming standard deviation of ciprofloxacin is 0.600 and standard deviation for BI 730357 is 0.15 when the sample sizes in the two groups are 12 and 27, respectively (nQuery Advisor, version 7). Using the same assumptions and calculation for 12 ciprofloxacin and 9 placebo instead of 27 BI 370357 subjects the power is 86%. Based on the similar study of pradigastat, the drop-out rate will be minimal. Further details will be discussed in the TSAP.

c27983101-03 Clinical Trial Protocol Page 68 of 79

Proprietary confidential information © 2020 Boehringer Ingelheim International GmbH or one or more of its affiliated companies

8. INFORMED CONSENT, TRIAL RECORDS, DATA PROTECTION, PUBLICATION POLICY, AND ADMINISTRATIVE STRUCTURE

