The alternative hypothesis will be that the means are not equal:

Alternative hypothesis H_a : $\mu_{\text{BI/pbo}} - \mu_{\text{cipro}} \neq 0$

A significant finding of increased photosensitivity of ciprofloxacin compared to BI 730357 400 mg QD and to placebo QD at the $p<0.05$ level will be supportive in concluding that the trial was appropriately designed to test the photosensitivity of BI 730357 400 mg QD.

15.3.2. 300 MG BID Dose Cohort

For comparisons of BI 730357 300 mg BID vs placebo BID, BI 730357 300 mg BID vs ciprofloxacin, and placebo BID vs ciprofloxacin, null and alternative hypotheses will be identical to the respective null and alternative hypotheses described above for the 400 mg QD dose cohort.

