15.4. PRIMARY ENDPOINT ANALYSIS OF PHOTOSENSITIVITY INDEX

400 mg QD Dose Cohort:

The primary analysis will be based on FAS for both conditions 1 and 2 at the 24 hour assessment.

Least squares (LS) mean for the difference between BI 730357 400 mg QD and placebo QD along with the corresponding 2-sided 90% CI will be obtained from the MMRM described in Section 15.2 above.

Absence of photosensitivity between BI 730357 400 mg QD and placebo QD will be concluded if the 2-sided 90% CI is fully contained within the acceptance range (-0.4, 0.4).

A significant finding of increased photosensitivity of ciprofloxacin compared to BI 730357 400 mg QD and to placebo QD at the $p<0.05$ level will be supportive in concluding that the trial was appropriately designed to test the photosensitivity of BI 730357 400 mg QD.

Document: L:\BIOS\Boehringer_Ingelheim_Pharmaceuticals\BI730357\1407-0037_MZA56588\Biostatistics\Documentation\SAP

Author: [REDACTED] Version Number: Final V2.0
Version Date: 23JUL2020

Template No: CS_TP_BS016 – Revision 5
Effective Date: 01Apr2018

Reference: CS_WI_BS005

Additionally, descriptive statistics by treatment will be provided for the primary endpoints.

For Conditions 1 and 2, figures of LS mean PI (+/- standard error [SE]) versus time points will be provided.

300 mg BID Dose Cohort:

The primary endpoint analysis of PI for the 300 mg BID dose cohort will be identical to that described above for the 400 mg QD dose cohort. Comparisons of BI 730357 300 mg BID vs placebo BID, BI 730357 300 mg BID vs ciprofloxacin, and placebo BID vs ciprofloxacin will be performed.

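### The supportive statement that the trial was properly designed includes ciprofloxacin versus BI 730357, so the chance of meeting it falls as the BI 730357 effect grows, even when the assay works

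*Protocol*

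**What the plan says.** Protocol 7.1 plans ciprofloxacin comparisons against BI 730357 and against placebo for each dose group, and then gives one sentence on what they say about the trial itself: "A significant finding of increased photosensitivity of ciprofloxacin compared to BI 730357 and to placebo at the p<0.05 level will be supportive". SAP 15.3.1 carries this over for the first cohort as "increased photosensitivity of ciprofloxacin compared to BI 730357 400 mg QD and to placebo QD". SAP 15.4 repeats it under the primary endpoint analysis, where the finding is called "supportive in concluding that the trial was appropriately designed to test the photosensitivity of BI 730357 400 mg QD". SAP 15.3.2 and the last part of 15.4 apply the same to 300 mg BID by reference.

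Protocol 7.5 gives the power. For ciprofloxacin versus BI 730357 the test "will have 87% power to detect a difference in means of 0.6". The means behind that figure are 1.60 for ciprofloxacin and 1.0 for BI 730357, the SDs 0.60 and 0.15, and the group sizes 12 and 27. For ciprofloxacin versus placebo, with 12 and 9 subjects and the same assumptions, the stated power is 86%.

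The primary conclusion does not use ciprofloxacin. Under SAP 15.4, absence of photosensitivity is concluded when the 90% CI for BI 730357 minus placebo lies within (-0.4, 0.4).

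**The concern.** A positive control answers one question: would this method have shown a photosensitising effect had there been one? Ciprofloxacin against placebo answers it, because neither arm contains the test drug. Ciprofloxacin against BI 730357 does not. That difference shrinks if BI 730357 is itself photosensitising, however well the assay performs. The 87% quoted for it holds only at a BI 730357 mean of 1.0, that is, with no effect.

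An effect is not remote here. Protocol 1.2 and 1.3 say that preclinical data indicate phototoxicity potential, and protocol 11.2 adds 300 mg BID to reach higher exposures. SAP 15 uses the same ciprofloxacin group for both cohorts. The same ciprofloxacin data could therefore support the design for one dose and not for the other, only because BI 730357 has a larger effect at the second dose.

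What is at stake is how the report reads. Neither document says how to interpret ciprofloxacin above placebo but not above BI 730357. A reader could take that as doubt about the assay, when it may mean that BI 730357 lies closer to ciprofloxacin.

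**Working it through.** **Inputs (protocol 7.5 and 7.1).** Ciprofloxacin mean PI 1.60, SD 0.60, n = 12. BI 730357 mean 1.0 with no effect, SD 0.15, n = 27. Placebo taken at mean 1.0, SD 0.15, n = 9 (7.5 applies the same assumptions). Two-sided 0.05 tests; equivalence limit 0.4. The true BI 730357 minus placebo effect is my assumption, varied from 0 to 0.6; at 0.6 BI 730357 equals ciprofloxacin.

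**Step 1: reproduce the stated power.** Satterthwaite (Welch) test, SE = √(s₁²/n₁ + s₂²/n₂).

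- Against BI 730357: SE = √(0.36/12 + 0.0225/27) = 0.1756; noncentrality 0.6/0.1756 = 3.417; df 11.6; power 87.8% (stated 87%).
- Against placebo: SE = √(0.36/12 + 0.0225/9) = 0.1803; noncentrality 0.6/0.1803 = 3.328; df 12.8; power 86.7% (stated 86%).

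Both stated figures reproduce.

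**Step 2: let BI 730357 have an effect e.** The noncentrality against BI 730357 becomes (0.6 − e)/0.1756: 2.278 at e = 0.2, 1.139 at 0.4 and 0 at 0.6. The power of that contrast is then 55%, 18% and 2.5%. The placebo contrast does not contain e and stays at 86.7%.

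**Step 3: the probability that both parts are met.** The contrasts share the ciprofloxacin arm, so I simulated them jointly (400,000 trials per scenario, counting significance only where ciprofloxacin is higher). The Welch version matches protocol 7.5. The second version pools one variance over the three arms, because the PROC MIXED code in SAP 15.2 has no group-specific covariance. It is a single-timepoint approximation to that model: pooled variance (11×0.36 + 26×0.0225 + 8×0.0225)/45 = 0.105, with 45 df.

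| Assumed BI 730357 effect | Both parts, Welch | Placebo part alone, Welch | Both parts, shared variance | Placebo part alone, shared variance |
|---|---|---|---|---|
| 0 | 85% | 87% | 95% | 95% |
| 0.1 | 74% | 87% | 93% | 95% |
| 0.2 | 55% | 87% | 84% | 95% |
| 0.3 | 35% | 87% | 67% | 95% |
| 0.4 | 18% | 87% | 45% | 95% |
| 0.6 | 2.5% | 87% | 11% | 95% |

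With the cited-study values in protocol 7.5 (ciprofloxacin 1.61, SD 0.55; placebo 1.08, SD 0.12; BI 730357 SD kept at 0.15), Welch tests meet both parts in 82%, 47% and 11% of trials at effects of 0, 0.2 and 0.4. The placebo part alone is met in about 84.5%. The pattern is the same.

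**Step 4: how often the mixed result accompanies a primary equivalence conclusion.** The awkward case is equivalence concluded, ciprofloxacin above placebo, and the BI 730357 part not met. With Welch tests, and equivalence judged on the variance pooled over BI 730357 and placebo, it occurs in 13%, 30%, 24% and 3% of trials at effects of 0.1, 0.2, 0.3 and 0.4. With one shared variance throughout it occurs in about 2%, 4%, 1% and 0%. The shared variance widens the equivalence interval, so at an effect of 0.2 equivalence is concluded in about 47% of trials instead of 96%.

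**The case against.** The strongest reply has four parts.

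1. The wording is permissive. A reader might infer that ciprofloxacin must exceed BI 730357, or that missing this means the assay failed. The documents support neither. They say that a significant finding is supportive; they set no pass/fail rule and attach no consequence to its absence. This stands.
2. The right contrast is already there. Placebo versus ciprofloxacin is listed as a planned comparison for each dose group in protocol 7.1, repeated in SAP 15.4 and 15.5, and has its own power in protocol 7.5. A report would show it. This stands, and it is why the correction needs no new analysis.
3. Large effects largely take care of themselves. At a true effect of 0.4 or more, equivalence is concluded in 5% of trials or fewer, and a clear BI 730357 minus placebo difference would itself show that the method detects photosensitivity. This limits the harm. It does not make the BI 730357 contrast evidence about the assay.
4. The size depends on the variance model. Under the model closer to the SAP code the loss is smaller, and the awkward case with equivalence concluded is at most about 4%, against 30% with Welch tests. This stands, so both sets of figures have to be shown.

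A reader might also infer that any real BI 730357 effect would make a working assay look as if it had failed. That goes too far: the loss is graded. At an effect of 0.1 both parts are still met in 74% of trials (Welch) or 93% (shared variance).

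None of this explains why a statement about design validity should rest partly on the test drug.

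**Conclusion.** The point holds as a flaw in what the supportive statement contains. One of its two parts measures the BI 730357 effect, so the chance of meeting it falls between effects of 0 and 0.4 from 85% to 18% (Welch) or from about 95% to 45% (shared variance), while ciprofloxacin separates from placebo at an unchanged rate. It does not affect the primary conclusion, the sample size or the error rate of the equivalence test. The consequence is a possibly misleading reading of assay validity, in either cohort.

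The figures rest on the protocol 7.5 means and SDs, on normal PI values at a single timepoint without dropout, and on BI 730357 effects that I assumed; the documents give no expected effect other than 0. The direction does not depend on the variance model. The size does.

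**What to change.** In protocol 7.1, strike the reference to BI 730357 from the supportive sentence, so that it rests on ciprofloxacin versus placebo only, and name the 24 h assessment for each condition. Make the cohort-specific equivalent change in SAP 15.3.1 and 15.4; 15.3.2 and the 300 mg BID part of 15.4 then follow by reference. Keep BI 730357 versus ciprofloxacin, with its CI, as a separate comparison that shows where BI 730357 stands relative to a known mild photosensitiser. In protocol 7.5, label the existing 86% (12 versus 9) as the power of the assay-sensitivity check.

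The cost is wording in two documents. No data, analysis or planned comparison is added or dropped, and the sample size is unchanged. The one downside is that the power quoted for the check is 86% and not 87%.

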7.2 PLANNED ANALYSES

7.2.1 General considerations

Analysis sets

Statistical analyses will be based on the following analysis sets:

- Treated set (TS): The treated set includes all subjects who were randomized and treated with at least one dose of study drug. The treated set will be used for safety analyses.
- Full analysis set (FAS): This set includes all subjects in the treated set (TS) who provide at least one photosensitivity endpoint that was defined as primary or secondary and was not excluded due to a protocol deviation relevant to the evaluation

c27983101-03 Clinical Trial Protocol Page 64 of 79

Proprietary confidential information © 2020 Boehringer Ingelheim International GmbH or one or more of its affiliated companies

of photosensitivity. Descriptive and model based analyses of photosensitivity endpoints will be based on the FAS.

Additional analysis sets, refinements of the above definitions, or other relevant details may be specified in the TSAP. The implications that patients with important protocol deviations (including receiving incorrect medication) might have on the analysis will be discussed at the report planning meeting(s) and decisions will be documented in the decision log.

7.2.2 Primary endpoint analyses

Photosensitivity index (PI)

The photosensitivity index (PI) under conditions 1 and 2 is the measurement used for the primary endpoints. It is defined as the ratio of the precise $MED_{baseline}$ to the $MED_{on-drug}$ (see Section 5.1) at each respective post-irradiation timepoint. Therefore, there will be $MED_{baseline}$ at 10 min, 1h, and 24h that will be used for the respective PI calculations, PI_{10min} , PI_{1h} , and PI_{24h} . For example, the PI_{1h} will be the precise $MED_{baseline}/MED_{on-drug}$ where each MED was measured at the 1 hour post-irradiation time point. The two primary endpoints are PI at 24 hours under conditions 1 and 2.

A mixed model for repeated measures on PI values will be utilized for the analysis. The model will include treatment (BI 730357, Placebo, ciprofloxacin), time (10min, 1h, 24h, 48h, and 72h), and treatment-time interaction as fixed effects and subject as a random effect. Adjusted means and differences in PI and 90% CIs for the 2 contrasts of interest (i.e. BI 703357 – placebo at 24h) will be calculated from the model.

The analysis will be carried out separately for condition 1 and condition 2.

Additional details, including the full specification of the FAS (if needed) and the handling of patients who may not have post-baseline data, will be included in the TSAP.

